8.3.2 Secondary Efficacy Analyses

The secondary efficacy analyses will include additional analyses of the primary efficacy endpoint as well as other analyses of the secondary endpoints, as outlined below.

The primary efficacy analysis will be repeated on the PP population.

Secondary analyses of the primary endpoint will be completed using individual two-sample t-tests and 95% t-distribution confidence intervals for each comparison (each netarsudil group vs placebo) using the ITT and PP populations.

Similar analyses will be completed on the secondary endpoints based on the ITT and PP populations: mean change from baseline in mean diurnal IOP at each post-treatment visit, mean IOP at each post-baseline time point, and mean change from diurnally adjusted baseline IOP at each post-treatment time point. Models adjusting for baseline will only be performed on the mean IOP response variable as inference is identical between this response and the change from baseline IOP response variable in such a model based on the PP and ITT populations.

Additionally, for the mean IOP values at each post-treatment time visit, mixed model repeated measures will be run with mean IOP baseline as the covariate; treatment, visit, time point, treatment by visit, treatment by time point, and treatment by visit by time point as the fixed effects; and subject as the repeated measure. An unstructured covariance structure will be used model covariances. This model will be run including the Week 1, Week 2, and Week 4 visits based on the ITT population only.

Graph will also be provided for mean IOP values by treatment group, visit, and time point.

Percent change from baseline in mean diurnal IOP at each post-treatment visit and percentage change from diurnally adjusted baseline IOP at each post-treatment time point will be analyzed using two-sample t-tests, between each netarsudil group and placebo, at each time point and visit, including two-sample t-tests and 95% t-distribution confidence intervals on the difference (netarsudil – placebo). The analysis will be based on ITT population only.

Analyses of IOP will also include summarizing the number and percentage of study eyes achieving mean diurnal IOP reduction from baseline of ≥ 4 to ≥ 12 mmHg in 2 mmHg increments and percent reduction from baseline of $\geq 5\%$ to $\geq 40\%$ in 5% increments at Week 1, Week 2, and Week 4. Additionally, the number and percentage of study eyes attaining a mean diurnal IOP of ≤ 22 to ≤ 14 mmHg in 1 mmHg increments will be summarized at Week 1, Week 2, and Week 4. Fisher's exact test (2-sided p-values) will be used to test the pair wise differences between treatment groups for each category at each visit. These analyses will be presented for the ITT population only.

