2.2 Overall Study Design and Plan

This is a 28-day, double-masked, randomized, multicenter, placebo-controlled, parallel-group efficacy and safety study evaluating elevated intraocular pressure (IOP) with netarsudil ophthalmic solution. The purpose of this study is to assess the efficacy and safety of netarsudil ophthalmic solution (0.02% and 0.04%) compared to its placebo in Japanese or Japanese-American subjects that are at least 18 years of age with open-angle glaucoma (OAG) or ocular hypertension (OHT).

All investigational products will be dosed in both eyes (OU) once daily (QD) in the evening (PM). Subjects eligible to be enrolled in this study will be those of Japanese ethnicity within the second generation, with a diagnosis of either OAG or OHT that are on treatment with a topical ocular hypotensive medication. A total of approximately 180 subjects will be enrolled in this study at approximately 35 clinical sites, all in United States, comprising a total of approximately 60 subjects per treatment arm for each of 3 treatment arms. Subjects who are enrolled in this study will be those at least 18 years of age with diagnosed OAG or OHT, each of whom meets all inclusion criteria and none of the exclusion criteria.

There will be a total of 6 visits designated as V1 – V6. For visits 3, 4, 5, and 6, the subjects will be evaluated at multiple time points (08:00, 10:00, and 16:00 hours) within the visit day. These time points will be designated as visit x.0, x.1, and x.2 respectively. The total treatment period is 28 days, starting at Visit 3 (Day 1), and there are follow-up visits at Week 1, Week 2, and Week 4.

At Screening (Visit 1), an examination will be conducted, including measurements of heart rate and blood pressure (vital signs), urine pregnancy test (for women of child bearing potential), and an ophthalmic examination to include ocular symptoms, best corrected visual acuity (BCVA), central corneal thickness by pachymetry (may be taken within 1 week of Visit 1), intraocular pressure (IOP; before pupil dilation. Medicated IOP must be ≥ 15 mmHg and < 30 mmHg in both eyes at the Screening Visit (this also applies to treatment naïve subjects), biomicroscopy, and dilated ophthalmoscopy). Visual fields and gonioscopy may be taken up to three months

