Due to the early study closure, the sample size is expected to be approximately 10 ITT subjects per arm. The study will not be able to achieve the adequate power for primary hypotheses as planned. Therefore, the analyses will be performed based upon the observed data for informational purposes only. No statistical inference will be made. No subgroup analyses will be performed.

There will be no adjustment for the multiplicity of the 2 active concentrations (0.02% and 0.04%) tested against placebo in this Phase 2 study.

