Mean diurnal IOP at Week 1 and Week 2	X	X			ITT	Observed data
Mean change from baseline in mean diurnal IOP at each post-treatment visit	X				ITT, PP	Observed data
Mean percent change from baseline in mean diurnal IOP at each post-treatment visit	X				ITT	Observed data
Mean IOP at each post-treatment time point	X	X			ITT, PP	Observed data
Mean IOP at each post-treatment time visit			X		ITT	Observed data
Mean change from diurnally adjusted baseline IOP at each post-treatment time point	X				ITT, PP	Observed data
Mean percent change from diurnally adjusted baseline IOP at each post-treatment time point	X				ITT	Observed data
Percentages of subjects achieving pre-specified mean, mean change, and percent mean change diurnal IOP levels				X	ITT	Observed data
^a Two Sample T-test comparing actual mean IOP value at each time point between each netarsudil group and placebo. ^b ANCOVA model including treatment as the main effect and baseline as the covariate. Individual models will be fit for each visit and time point. ^c Mixed Model Repeated Measures analysis including treatment as the main effect, and baseline IOP, visit, time point, treatment*visit, treatment*time point, visit*time point, and treatment*visit*time point as model terms. Repeated measures will be used to account for the correlation among measures within a subject. The model will include all post-dose visits and time points. ^d Fisher's exact test comparing the incidence in each category at each time point between each netarsudil group and placebo.						

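### SAP 8.3.2 leaves visit by time point out of the repeated-measures model and names no small-sample method, so the three-way interaction p-value can mislead (minor)

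*SAP*

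**What the plan says.** SAP Section 8.3.2 plans a mixed model for repeated measures on IOP. The fixed effects, besides baseline, are "treatment, visit, time point, treatment by visit, treatment by time point, and treatment by visit by time point as the fixed effects". On the covariance it says: "An unstructured covariance structure will be used model covariances". On scope: "This model will be run including the Week 1, Week 2, and Week 4 visits based on the ITT population only". Subjects are "evaluated at multiple time points (08:00, 10:00, and 16:00 hours) within the visit day", so there are nine repeated measures per subject.

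Footnote c of SAP Table 8-1 describes the same model with one more term: "treatment*visit, treatment*time point, visit*time point, and treatment*visit*time point as model terms". Protocol Section 9.6.2 also lists visit by time point. SAP Section 13, which records changes from the protocol, does not mention dropping it.

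SAP Section 8.2 says that, because of early closure, "the sample size is expected to be approximately 10 ITT subjects per arm". Neither document names a denominator df method or a small-sample correction for this model. The sample SAS code in protocol Appendix 7 is for the single-visit ANCOVA and sets no df option. SAP Section 8.3 keeps two-sided 5% tests, while Sections 8.2, 8.3.1 and 13 label the efficacy results as informational and rule out inference.

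**The concern.** There are two separate problems.

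**The omitted term.** A programmer who follows the 8.3.2 text fits a different parameterisation from one who follows Table 8-1. Without visit by time point, the three-way term has to carry any change in the daily IOP curve between visits that is common to all arms. Its test then no longer concerns treatment alone and can be significant when treatment does nothing.

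**The small sample.** The covariance structure comes from a plan for 180 subjects. The SAP cut other analyses after early closure (imputation and subgroups) but left this structure unchanged. With about 30 subjects, a Wald F test that ignores the uncertainty in 45 estimated covariance parameters can reject too often. The excess grows with the numerator df and depends on a df method that the SAP does not state.

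At stake is a small three-way p-value being read as a visit-specific or time-of-day drug effect that is not there.

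**Working it through.** **Plan's own figure first.** SAP Section 2.6 gives SD 3.5 mmHg per time point, correlation 0.60 and a 2.0 mmHg difference. The SD of the diurnal mean is 3.5 × √((1 + 2 × 0.6)/3) = 2.997, stated as 3.0. The two-sample t calculation gives 90.4% power at 49 per arm and 95.2% at 60, against the stated 90% and 95%. These figures reproduce, so the same SD and correlation are used below. The documents give no operating figure for the repeated-measures model.

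**Parameter counts.**
- Repeated measures: 3 visits × 3 time points = 9. Covariance parameters: 9 × 10/2 = 45.
- Subjects: about 3 × 10 = 30.
- Full model as in Table 8-1: 1 (intercept) + 2 (treatment) + 2 (visit) + 2 (time point) + 4 + 4 + 4 (two-way terms) + 8 (three-way) = 27 cell means, plus baseline = 28 fixed effects.
- Model as in the 8.3.2 text: the lower-order terms use 1 + 2 + 2 + 2 + 4 + 4 = 15. The three-way term spans the remaining 27 − 15 = 12 df.
- The rank is 27 in both cases. Fitted cell means, least squares means and treatment contrasts are therefore identical; only the content of the three-way test changes.

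**Simulation set-up.** No treatment effect; 10 per arm; SD 3.5; correlation 0.6 throughout, including with a subject-level baseline covariate; REML with the 9 × 9 unstructured matrix. Because the SAP names no df method, three were tried: between-subject (30 − 3 − 1 = 26), residual (30 × 9 − 28 = 242) and infinite.

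**Rejection rates at nominal 5%, complete data, 4,000 runs, no visit-by-time pattern.**

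| Test | Between-subject df | Residual df | Infinite df |
|---|---|---|---|
| Treatment (2 df) | 4.7% | 6.5% | 6.7% |
| Treatment by visit (4 df) | 5.1% | 7.9% | 8.3% |
| Treatment by time point (4 df) | 5.6% | 8.4% | 8.9% |
| Three-way, correct (8 df) | 7.7% | 13.7% | 14.3% |
| Single Week 4 diurnal contrast | 4.9% | 5.9% | 6.0% |

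A separate set of 800 runs put the 8-df test lower, at 5.6 / 10.5 / 11.5%. A direct check with 40,000 draws of the test statistic on 27 error df gave 7.8% for the between-subject case, which supports the larger set. With an assumed 15% dropout (1,500 runs) the 8-df test rose to 10.3 / 16.7 / 18.1%. At 60 per arm with complete data, the treatment and interaction tests lay between 4.6% and 6.4%.

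**Effect of the omitted term.** A visit-by-time pattern common to all arms was added at the four corner cells of the visit by time point grid, again with no treatment effect. The documents give no such pattern, so two sizes are shown as assumptions.

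| Common pattern | 12-df test from the 8.3.2 text: between-subject / residual / infinite df |
|---|---|
| ±0.5 mmHg | 28 / 44 / 46% |
| ±1.0 mmHg | 87 / 94 / 94% |

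In the same settings the correct 8-df test rejected in 7 to 14%. These rates are plausible. The within-subject variance is 3.5² × (1 − 0.6) = 4.9, so a pure interaction pattern gives a noncentrality of 30 × 4 × 0.5²/4.9 = 6.1, or 30 × 4 × 1.0²/4.9 = 24.5.

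**After the fix.** Kenward-Roger, complete data, 1,500 runs (Monte Carlo standard error about 0.6 points): three-way 8-df 5.2%, treatment by visit 5.8%, treatment by time point 4.9%, treatment 4.4%.

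**The case against.** The strongest reply is that little depends on this model. The SAP says that no inference will be made, the model is secondary and run on ITT only, and the ANCOVA and t-tests by visit and time point already give the simple comparisons. This stands and sets the severity. It does not remove the point, because Section 8.3 still calls for nominal 5% tests and an informational p-value should at least refer to the right hypothesis.

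A second reply is that the missing term is a slip of text, since Table 8-1 and the protocol have it. That is probably so. But SAP Section 3 only lets specific sections override its own general policies. It does not rank Section 8.3.2 against the table, so the conflict remains.

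A third is that the SAP never says the interaction F tests will be reported, and protocol Section 9.6.2 presents the interactions as model flexibility. This also stands: the harm arises only if the three-way test is produced.

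A reader might infer more than the documents support:
- *That all multi-df tests from this model are anti-conservative.* With complete data and between-subject df, treatment and both two-way tests with treatment are near nominal (4.7-5.6%). Inflation there depends on the df method or on dropout, and neither is stated.
- *That a joint comparison of all nine cells with placebo is badly inflated.* Neither document plans such a test.
- *That the unstructured matrix must be replaced.* Every fit converged where this was tracked (800 complete-data runs, 1,500 with 15% dropout), and Kenward-Roger alone restored the three-way test with complete data. A visit-by-time product structure would add a separability assumption, whereas the protocol chose unstructured to avoid such restrictions.

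**Conclusion.** The point holds in limited form, with minor severity. The 8.3.2 text contradicts Table 8-1 and the protocol. If the text is followed, the three-way test has 12 df instead of 8 and can reject often with no treatment effect: 28-46% for a ±0.5 mmHg common pattern and 87-94% for ±1.0 mmHg, depending on the df method. Independently, the correct 8-df test rejects about 7-8% with between-subject df and complete data, about 14% with residual or infinite df, and more with dropout.

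Only the three-way test is mis-targeted. Single-contrast tests are near nominal with between-subject df and complete data.

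The percentages rest on assumptions: a common correlation of 0.6 across visits and with baseline, 10 subjects per arm, dropout of 0 or 15%, and pattern sizes that the documents do not give. The change from 8 to 12 df rests on none of these.

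**What to change.** 1. Add visit by time point to the fixed effects in SAP Section 8.3.2, so that it agrees with Table 8-1 footnote c and protocol Section 9.6.2.
2. Specify Kenward-Roger standard errors and denominator df for this model.
3. Keep the unstructured covariance, and name a simpler structure in advance to be used only if the model does not converge.
4. State which outputs of the model will be reported (least squares mean differences by visit and time point, interaction tests, or both).

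The cost is one model term, one option and two sentences. P-values for the multi-df tests become slightly larger. Kenward-Roger does not replace step 1: it corrects the calibration of a test, not the hypothesis being tested. Its 5.2% was obtained with complete data only.

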2.6 Sample Size Determination

Assuming a 2-sided test with $\alpha = 0.05$ and a common standard deviation (SD) of 3.5 mmHg at each time point yielding a common SD of 3.0 for the diurnal mean assuming a correlation among time points of 0.60, 49 ITT subjects per arm yields at least 90% power to demonstrate superiority of netarsudil (0.02% or 0.04%) to placebo in mean diurnal study eye IOP (average of 08:00, 10:00, and 16:00 hours) at the Week 4 visit assuming a difference of at least 2.0 mmHg in the mean diurnal IOP. The study will be considered a success and superiority of netarsudil to placebo will be concluded if the two-sided p-value ≤ 0.05 at Week 4. With 60 intent-to-treat (ITT) subjects per arm, each test has 95% power to demonstrate superiority of netarsudil (0.02% or 0.04%) to placebo.

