6. DEMOGRAPHIC AND OTHER BASELINE CHARACTERISTICS

6.1 Demographics and Baseline Characteristics

Demographic and baseline characteristics will be summarized by treatment group and listed for the randomized population. Demographic parameters will include sex, age in years at signing of informed consent form (ICF), Japanese ethnicity (1st or 2nd generation), prior hypotensive therapy, and time on current hypotensive therapy. Baseline characteristics will include study eye diagnosis of OHT or OAG, length of time since study eye diagnosis of OHT or OAG, study eye IOP at screening, and study eye mean diurnal IOP at baseline. Additionally, means for both the study eye and the fellow eye will be summarized separately for the baseline ocular measurements of deviation in visual fields, central corneal thickness, and cup-to-disc ratio.

Age will be reported in years and calculated in SAS using the formula:

$$\text{Age} = \text{Floor}((\text{ICFDT} - \text{DOB}) / 365.25)$$

where ICFDT is the date the subject signed the informed consent, DOB is the subject's date of birth, and Floor takes the integer part of the result.

Tests of differences between the treatment groups will be performed for both demographic and baseline characteristics. Categorical responses will be tested using Fisher's exact tests. Continuous measures will be tested using an analysis of variance model with treatment as the only explanatory variable.

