8.3.1 Primary Efficacy Analyses

Only observed data will be used for efficacy analyses. The primary analysis of the primary outcome will employ a linear model with mean diurnal IOP at Week 4 as the response, baseline mean diurnal IOP as a covariate, and treatment as a main effect, using the ITT population. The treatment differences (netarsudil – placebo) between each netarsudil group and placebo will be

tested. The least squares mean differences (netarsudil – placebo) will be presented separately for netarsudil 0.02% and 0.04% as well as 2-sided p-values and 95% confidence intervals (CIs). However, no statistical inference will be made.

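### Both percent-change IOP endpoints get only unadjusted t-tests; the three-arm ANCOVA already in the SAP could be added beside them at little cost

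*SAP*

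**What the plan says.** SAP 8.3.2 assigns both percent-change endpoints one method: they "will be analyzed using two-sample t-tests, between each netarsudil group and placebo, at each time point and visit", in the ITT population. In Table 8-1 the rows for these endpoints, for example "Mean percent change from diurnally adjusted baseline IOP at each post-treatment time point", are marked for the t-test only. Protocol 9.6.2 plans the same. The term diurnally adjusted refers to a time-matched baseline (SAP 3 and 8.3), not to a covariate.

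Baseline adjustment is planned elsewhere. The primary model in SAP 8.3.1 has "baseline mean diurnal IOP as a covariate, and treatment as a main effect, using the ITT population", with LS mean differences for both concentrations. Table 8-1 extends the ANCOVA to mean diurnal IOP at Weeks 1 and 2 and to mean IOP at each time point; footnote b says "Individual models will be fit for each visit and time point". The sample code in Protocol Appendix 7 has treatment as one factor across all arms.

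SAP 8.3.2 confines adjusted models to mean IOP "as inference is identical between this response and the change from baseline IOP response variable". SAP 6.1 tests the arms for differences in baseline characteristics, including "study eye IOP at screening, and study eye mean diurnal IOP at baseline". After early closure, SAP 8.2 states that "the sample size is expected to be approximately 10 ITT subjects per arm" and that results are informational, without inference.

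**The concern.** The SAP's reason for limiting adjusted models is correct for the endpoints it names. Subtracting baseline from the response, with baseline already in the model, leaves the treatment contrast and its standard error unchanged. Percent change, 100 × (Week 4 − baseline) / baseline, is not a linear shift of Week 4 IOP, so that equivalence does not carry over. The SAP gives no other reason specific to percent change.

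With about 10 subjects per arm, chance differences in baseline IOP are likely, and percent change can still depend on baseline after division by it. The baseline comparison in SAP 6.1 would show such an imbalance but would not correct the percent-scale estimate. When results are informational only, the estimate and its confidence interval are the product, so a cheap gain in precision is worth considering.

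**Working it through.** **The plan's own figures.** SAP 2.6 assumes "a common standard deviation (SD) of 3.5 mmHg at each time point yielding a common SD of 3.0 for the diurnal mean", with correlation 0.60 among time points. SD of the diurnal mean = 3.5 × √((1 + 2 × 0.60)/3) = 2.997, which agrees with 3.0. For a 2.0 mmHg difference at two-sided 0.05, noncentral-t power is 90.4% at 49 per arm and 95.2% at 60 per arm, as stated. At 10 per arm it is about 29%.

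**Degrees of freedom at 10 per arm.** The pairwise t-test has 20 − 2 = 18 error df (critical value 2.101). The three-arm ANCOVA has 30 − 4 = 26 (2.056).

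**Dependence of percent change on baseline.** To first order the slope is

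100 × (r × SD_Y/SD_B − mean_Y/mean_B) / mean_B,

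where Y is Week 4 IOP and B is baseline. Assume mean_B = 20, both SDs 3.0, r = 0.6, and mean changes of −1 mmHg (placebo) and −3 mmHg (both netarsudil arms):

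- Placebo: 100 × (0.6 − 19/20)/20 = −1.75 points per mmHg.
- Netarsudil: 100 × (0.6 − 17/20)/20 = −1.25 points per mmHg.
- Three-arm average: about −1.4 (simulated −1.38).

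The standard error of a baseline difference between two arms is 3.0 × √(2/10) = 1.34 mmHg. An imbalance of that size moves the unadjusted difference by 1.34 × 1.38, about 1.8 percentage points. ANCOVA removes this.

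The arms' slopes differ by 100 × 2/20² = 0.5 points per mmHg at mean 20 and 100 × 2/22² = 0.4 at mean 22, so a common slope is approximate. The slope falls to zero when r × SD_Y/SD_B is near mean_Y/mean_B (0.85 to 0.95 at mean 20). There the covariate gains nothing.

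**Simulation.** 8,000 three-arm trials per setting, 10 per arm. Week 4 SDs are the SAP's (3.0 diurnal mean, 3.5 single time point). Assumed, because the documents do not give them: baseline mean 20 or 22 and SD 3 or 4 before truncation to 15–35 mmHg, r from 0.3 to 0.9, and the changes above. Entries are mean 95% CI width, three-arm ANCOVA divided by t-test.

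| Week 4 SD | Baseline mean/SD | r 0.3 | 0.5 | 0.6 | 0.7 | 0.8 | 0.9 |
|---|---|---|---|---|---|---|---|
| 3.0 | 20/3 | 0.888 | 0.943 | 0.970 | 0.989 | 1.001 | 0.984 |
| 3.0 | 20/4 | 0.818 | 0.875 | 0.900 | 0.926 | 0.950 | 0.974 |
| 3.0 | 22/3 | 0.856 | 0.915 | 0.943 | 0.968 | 0.990 | 1.001 |
| 3.0 | 22/4 | 0.775 | 0.830 | 0.851 | 0.876 | 0.898 | 0.909 |
| 3.5 | 20/3 | 0.928 | 0.977 | 0.994 | 1.003 | 0.990 | 0.914 |
| 3.5 | 20/4 | 0.873 | 0.930 | 0.956 | 0.979 | 0.998 | 1.001 |
| 3.5 | 22/3 | 0.903 | 0.960 | 0.982 | 0.997 | 0.999 | 0.949 |
| 3.5 | 22/4 | 0.835 | 0.894 | 0.925 | 0.948 | 0.975 | 0.992 |

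- Pooling the third arm's variance, without a covariate, gives 0.967 to 0.989 (SD 3.0) and 0.974 to 0.992 (SD 3.5), so it contributes about 1 to 3 points.
- The covariate alone gives 0.796 to 1.021 (SD 3.0) and 0.856 to 1.021 (SD 3.5).
- With half the eyes OHT (22–35) and half OAG (15–35), the overall ratios are 0.784 to 0.999 and 0.841 to 1.000.
- The two methods' mean treatment differences agree within about 0.1 percentage point throughout.

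**Absolute size.** At baseline 20/3 and Week 4 SD 3.0, with SDs and r defined before truncation, mean half-widths (t-test, then ANCOVA) are 15.3 and 13.5 points at r = 0.3, 13.1 and 12.2 at 0.5, 11.8 and 11.3 at 0.6, and 8.5 and 8.5 at 0.8. The true difference is about −10 points. This definition gives a ratio of 0.953 at r = 0.6, against 0.970 in the table. With no treatment difference, type I error at r = 0.3, 0.6 and 0.8 is 4.8% to 5.3% for the t-test and 4.8% to 5.4% for ANCOVA.

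**The case against.** The strongest reply is that nothing is broken. Protocol and SAP agree, the t-test is unbiased, and both methods estimate the same difference. Baseline-adjusted results are already planned in mmHg, by ANCOVA and by the repeated-measures model, and percent change already divides by each subject's own baseline. The sponsor chose to cut analyses after closure (SAP 13), no inference will be drawn, and SAP 1 and 11 allow supplementary analyses without a change to the plan. All of this stands and keeps the point small. Analyses added later, however, would not be pre-specified.

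The size of the gain is also open to challenge. The 23% figure comes from one corner of the grid: baseline 22/4, Week 4 SD 3.0, r = 0.3. With baseline SD set equal to Week 4 SD and r of 0.5 to 0.6, intervals are 2% to 9% narrower on average, or about 0.3 to 1.0 percentage point of half-width. This trial runs once, and in those settings the ANCOVA interval is wider than the t-test interval in about 25% to 39% of simulated trials; at r = 0.8, in about 43% to 47%. The unequal slopes cannot be checked well with 10 subjects per arm. These points limit the benefit. They do not make the addition unsound, because the t-test stays and the average width is at worst about equal.

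**Conclusion.** The point holds as an optional improvement of small consequence. The plan contains no baseline-adjusted estimate on the percent scale, and its stated reason for limiting adjusted models does not reach percent change.

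Across the assumed range the average interval is 0% to 23% narrower for the diurnal mean and 0% to about 16% narrower for time points. At r 0.5 to 0.6 these become 3% to 17% and 1% to 11%. At r of 0.7 or higher the gain is under 3% in 15 of 24 settings. Adjustment would also move the single-trial estimate by about 1 to 3 percentage points on average at r 0.5 to 0.6.

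These sizes depend on the assumed baseline distribution, changes and r. The 0.60 in SAP 2.6 is a correlation among time points within a day and does not establish r.

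**What to change.** In SAP 8.3.2 and Table 8-1, add for both percent-change endpoints, beside the t-test, the ANCOVA already specified: treatment plus the matching baseline (diurnal mean for the visit endpoint, time-matched for the time-point endpoint), three arms in one model, ITT, observed data. Report LS mean differences (netarsudil − placebo) with 95% CIs. Amend the sentence in 8.3.2 that confines baseline-adjusted models to mean IOP, so that the text and table agree.

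The full version needs 3 + 9 = 12 models and 12 × 2 = 24 differences. Limiting it to the diurnal mean needs 3 models and 6 differences and keeps most of the benefit. No new data are needed, and the model code is already planned. The costs are extra output in a deliberately shortened plan, one degree of freedom per model, an approximate common slope, and little or no gain if r is high.
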